**A Technology-Based Adaptive Intervention to Promote Cardiovascular Health after Completion of
Cardiac Rehabilitation (Mobile4Heart)**

[name], MS, FNP-BC, FAAN, FAHA

NCT03446313

Protocol Date: 02/23/2018

Background

While numerous studies have examined barriers to cardiac rehabilitation (CR) and patient outcomes immediately following CR, few have investigated long-term adherence to secondary prevention behaviors and outcomes of patients who complete CR. Ongoing maintenance of physical activity after CR is an important part of preventing secondary cardiac events in patients with ischemic heart disease. However, it is well-documented that after discharge from a CR program, many patients return to a sedentary lifestyle. Applying mobile health strategies as a method of increasing adherence by providing education and support holds much promise.

Close monitoring after CR completion has been shown to be an effective strategy for improving patient adherence to program recommendations. In addition, interventions involving continued communication between patient and health care provider post-immediate discharge decreases hospital readmissions. Post-CR monitoring through mobile technology may be an effective strategy for improving patient adherence.

Our central hypothesis is that monitoring and promotion of health-related behaviors by increasing patient-provider communication through a mobile device after discharge from a CR program increases adherence to a 'heart healthy' prescription over an extended period of time. Through a mixed-methods study design, we will examine the efficacy of mobile technology to promote secondary prevention behaviors including physical activity as an extension of an outpatient CR program. The intervention includes use of a mobile phone app (MVN) for physical activity and healthy lifestyle behaviors such as medication adherence, nutrition, stress management, smoking cessation, etc. We will apply an adaptive design that accounts for varying levels of adherence from baseline to 2 months (N=60).

The specific aims of this randomized clinical trial comparing the intervention group (MVN app and Fitbit) to the control group (pedometer only) will:

1. Evaluate differences in physical activity.
H₀: The MVN group will have more physical activity (measured by an activity tracker) and better 6 minute walk tests compared to Usual Care.
2. Determine differences in depression and self-efficacy to continue exercise.
H₀: The MVN group will have less depression and higher self-efficacy compared to Usual Care.
3. Assess usability and satisfaction with using a smartphone application for participation in a post-CR cardiac health program.
H₀: The MVN group will report high usability and satisfaction with the MVN app.

Study Design

Mixed methods study with a randomized controlled trial and usability study with individual interviews.

Selection of Subjects / Setting

We plan to enroll up to 60 participants from John Muir Medical Center (JMMC). JMMC is a non-profit, community hospital system consisting of two large medical campuses and 3 CR locations (Brentwood, Concord, Walnut Creek). Participants will be randomized through a computer program to either the intervention group (Mvn app) or control group (usual care).

Inclusion criteria:

1. ≥ 18 years of age
2. History of cardiovascular disease that qualified patient for cardiac rehabilitation (i.e., ischemic heart disease, history of unstable angina, systolic heart failure with ejection fraction =/ $< 35\%$ and Class II to IV symptoms, coronary artery bypass graft surgery, valve replacement)
3. Within eight weeks of completing outpatient cardiac rehabilitation

Exclusion criteria:

1. Cognitive impairment
2. Lack of English proficiency/literacy
3. Clinically conditions including:
 - a. Unstable arrhythmias, aortic stenosis, thrombophlebitis, dissecting aneurysm or symptomatic anemia
 - b. Active infection
 - c. Uncontrolled hypertension: resting diastolic > 100 mmHg, systolic > 180 mmHg
 - d. Decompensated heart failure NYHA Class 3-4
 - e. Current unstable angina (No chest pain for a month)
 - f. 2nd or 3rd degree heart block
 - g. Uncontrolled high grade exercise-induced ventricular ectopy-hemodynamically stable

Both Usual Care and MVN Intervention groups

- Upon completion of the CR program, participants will be given their standard instructions and educational handouts
- Individuals will meet with their nurse or other health care provider in an exit interview to review their exercise progress, discuss their future exercise goals and plans, and receive referrals to additional medical services they might need after discharge from the program.
- Baseline clinical measurements, including a 6 minute walk
- An activity tracker will be given to each participant. Participants randomized to the intervention group will receive a Fitbit and instructions on how to sync their data. Participants randomized to the control group will receive a basic pedometer with a paper diary to record their step counts each day.
- Questionnaires will ask about health care utilization, physical activity, quality of life, and self-efficacy.
- The clinical measurements and psychosocial questionnaires will be taken again at 2-months.
- Participants will be paid \$50 in the form of a gift card for each month they complete. Participants that participate in the individual interview will receive an extra \$25 card. Participants in the intervention group will be allowed to choose whether they would like to keep the Fitbit or receive the gift cards. Participants in the control group will be allowed to keep their pedometer and will also receive the gift cards. If a participant withdraws from the study before month two, they will be asked to return their devices.

MVN Group Only:

- During the final week of outpatient cardiac rehabilitation, the MVN application will be downloaded on to the participant's smartphone or tablet. If the participant does not have a smartphone or tablet, a smartphone will be provided to them for the duration of the study. The participant will be required to return the smartphone at the end of their participation in the study.

- Each participant's individualized instructions for post-cardiac rehabilitation will be integrated into the MVN application including daily medication reminders, physical activity prompts, educational materials, and patient-reported outcome assessment of behavior and psychosocial status.
- Text messages or phone calls will be used on an ad hoc basis to provide positive feedback to the participant. Frequency of messages will depend on adherence level (adaptive intervention).
- We will apply an adaptive intervention: a sequence of decision rules that specify how the intensity or type of treatment should change depending on the patient's needs. We are developing sequential, multiple assignment, randomized trials (SMART) to enable scientists to build adaptive interventions. Interventions that adapt at the right times can improve participant outcomes (e.g., intensifying for people who do not respond to the initial treatment) while decreasing the cost and burden of the intervention (e.g., stepping down treatment for responsive participants).
- Regular messages will be based on the American Heart Association Simple 7 Principles (3 times a week on random days and between 9am-6pm). Examples include prompting participants to engage in physical activity, track their medicine at certain times of the day, engage in healthy eating habits, or provide participants with a homework assignment to reinforce educational content regarding risk management.
- Any patient reports of chest pain or acute shortness of breath will immediately prompt an automated message on the app to call 911 or their cardiologist/primary care provider. The consent will specify the research members including nurse will only monitor app use but not play an integral role in provided one-on-one coaching.
- A registered nurse or nurse practitioner will be available to triage patient entries once a day (mid-afternoon). Two-way messaging between the participant and the nurse will be available to provide opportunities to answer more specific questions.
- Technical support will be provided by Moving Analytics who has developed and own the MVN app.
- We will assign patients to a group of 6 individuals to offer social support and a "buddy system", which will be a feature in the secure MVN app. Ideas for these groups may be sharing exercise tips/goals/progress, recipes, etc. The groups will be formed with consecutive enrollment. The function of the social group will be iterative with regular feedback from the group members that will be sent to the research assistant to improve this feature.
- Up to six participants from the intervention group will be asked to complete an individual interview to assess the feasibility of and their satisfaction with the mobile app over the two month period.

Study Activities:

Activity	Usual Care	MVN	Intervals
MVN mobile app		X	Intervention period
Educational materials	X	X	Baseline
Activity tracker	X	X	Intervention period
Step count diary	X		Intervention period
Physical activity prompts		X	Intervention period
Nurse feedback (through app or by phone)		X	Intervention period
Psychosocial questionnaires	X	X	Baseline, Month 2

Blood pressure/heart rate	X	X	Baseline, Month 2
Weight	X	X	Baseline, Month 2
6 minute walk	X	X	Baseline, Month 2

Intervention period: 2 months

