**[name], MS, FNP-BC, FAAN, FAHA**

**NCT03446313**

**Statistical Analysis**

**04/23/2019**

P-values for baseline tests were calculated from two-sample t-tests (or Wilcox rank-sum test if skewed) or chi-squared tests.

We analyzed the primary outcome of step count difference between the two groups over 60 days fitting linear mixed-effects models with the step count for each day in R (version 3.6.0). For a more precise estimate of the treatment effect, we used a step-wise procedure to include potential covariates impacting the outcome (age, gender, working status, college or higher education, relationship status, depression, self-efficacy, and self-reported PA), including only terms that were significant in the model. The 2-sided significance level was established a priori at an alpha of 0.05. We employed an intention-to-treat analysis approach. We tested our secondary outcome of the standardized change score in 6MWT from baseline and 2 months also using linear mixed models, with the same approach. The covariate association of depression and self-efficacy for step count difference and 6MWT were also considered to be secondary questions of interest.

Since our analysis included a small amount of missing data for the covariates (education missing on 8%, all other covariates <4%), our analyses used multiple imputation by chained equations, using 5 imputations. Results differed very little compared to complete case analysis.

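### No cardiac diagnosis or walking-capacity measure is in the covariate list, although eligibility admits systolic heart failure alongside ischaemic, bypass and valve patients: a modest loss of precision, not a bias

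*Protocol*

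**What the plan says.** **Eligibility.** Inclusion criterion 2 (Protocol, Selection of Subjects / Setting) requires a "History of cardiovascular disease that qualified patient for cardiac rehabilitation". Its examples are ischaemic disease, past unstable angina, bypass surgery, valve replacement, and systolic heart failure with an ejection fraction at or below 35% and Class II to IV symptoms. Exclusion 3d removes "Decompensated heart failure NYHA Class 3-4". Inclusion 3 limits entry to people within eight weeks of finishing outpatient rehabilitation.

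**Allocation.** The same section says "Participants will be randomized through a computer program to either the intervention group (Mvn app) or control group (usual care". It gives no ratio, blocking or stratification factor. Planned enrolment is at most 60.

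**Baseline measures.** The six-minute walk is done at baseline and month 2 in both arms. Activity trackers are handed out according to randomised group, and the Study Activities table lists them for the intervention period only. No step count from before the intervention is described.

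**Analysis.** The SAP states: "We analyzed the primary outcome of step count difference between the two groups over 60 days fitting linear mixed-effects models", using each day's count. The candidate covariates are "age, gender, working status, college or higher education, relationship status, depression, self-efficacy, and self-reported PA". A stepwise procedure keeps only those that reach significance. The six-minute-walk outcome, a standardised change score, is modelled in the same way.

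**The concern.** The primary outcome is the level of daily steps, and without a baseline step count the model cannot adjust for each person's starting level. Other baseline variables must then explain the differences between people. A participant with an ejection fraction of 35% or less may well walk less than one recovering from valve surgery, but the candidate list has no diagnosis, ejection fraction, functional class or baseline walk distance. The nearest candidate is self-reported activity, and the stepwise rule does not guarantee that it stays.

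Two things are at stake. Variance that a known baseline variable could explain remains in the standard error. And with about 30 per arm, a few more heart-failure patients on one side can move the estimated step difference, with nothing in the described analysis to show or correct it.

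**Working it through.** The documents give no power calculation, step-count SD, heart-failure share or heart-failure effect, so there is no figure of the plan's own to reproduce.

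**From the documents:** at most 60 participants; two-sided alpha 0.05.

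**Assumed:** 1:1 allocation (30 per arm); between-person SD 3,000 steps/day, using one mean per participant; heart-failure share *p* of 10%, 20% or 30% (K = 6, 12 or 18 of 60); heart-failure deficit *D* of 1,000 to 3,000 steps/day.

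**1. Size of chance imbalance.** With K heart-failure patients randomly split 30/30, the SD of the between-arm difference in proportion is (2/30) × √[30 × p × (1−p) × 30/59]. For p = 0.20 this is (2/30) × √(4.8 × 0.508) = 0.104. Tail probabilities come from the hypergeometric distribution.

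| Share | SD of imbalance | P(≥10 points) | P(≥20 points) |
|---|---|---|---|
| 10% | 7.8 points | 19.5% | 2.4% |
| 20% | 10.4 points | 33.3% | 10.4% |
| 30% | 11.9 points | 39.9% | 15.8% |

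Twenty points is a difference of six patients between arms of 30.

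**2. Effect on the unadjusted step difference.** Shift = imbalance × D. One SD gives from 0.078 × 1,000 = 78 to 0.119 × 3,000 = about 360 steps/day. A 20-point imbalance gives 0.20 × 1,000 = 200 to 0.20 × 3,000 = 600 steps/day.

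**3. Precision.** Unadjusted SE = 3,000 × √(2/30) = 775 steps/day. The share of between-person variance explained by the indicator is R² = p(1−p)D²/3,000², and the SE is multiplied by √(1−R²). Power is for an illustrative difference of 2,000 steps/day (unadjusted 73%).

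| Share, deficit | R² | SE multiplier | Power, adjusted |
|---|---|---|---|
| 10%, 1,000 | 0.010 | 0.995 | 74% |
| 20%, 2,000 | 0.071 | 0.964 | 76% |
| 30%, 3,000 | 0.210 | 0.889 | 83% |

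Steps 2 and 3 describe one loss, not two. In the middle row, √(775² − 208²) = 747, the same as 775 × 0.964 = 747, where 208 is 0.104 × 2,000.

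**4. Cost of the extra term.** The multipliers ignore the estimation of one more coefficient. Under random allocation the average squared correlation between arm and indicator is 1/59 (check: 0.104² × 0.25/0.16 = 0.017). The SE therefore rises by about √(59/58) − 1 = 0.9%. In the first row this cancels the gain (0.995 × 1.009 = 1.004). In the last row about 10% remains (0.889 × 1.009 = 0.897).

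**5. Type I error.** In 40,000 simulated trials for each of four settings (10% and 20% share with a 2,000-step deficit; 20% and 30% with 3,000), overall type I error was 4.8-5.2% unadjusted and 4.9-5.1% adjusted. Among trials with an imbalance of at least 20 points, the unadjusted rate was 7-8% (2,000-step deficit) or 11-12% (3,000-step deficit).

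No size was worked out for the six-minute-walk model, whose change-score outcome already removes part of the starting level.

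**The case against.** The strongest reply is that covariate choice is discretionary and that one plausible prognostic variable among many has been left out. Several parts of that reply stand.

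- **Chance imbalance is not bias.** Randomisation puts it into the standard error, and step 5 confirms that the overall error rate holds. A reader might infer that diagnosis mix distorts the comparison or invalidates the test; the documents do not support that.
- **The size is not anchored.** Share, deficit and SD are all assumed. At the low end the gain is nil.
- **The contrast is narrower than inclusion 2 alone suggests.** Exclusion 3d and completed rehabilitation both limit how impaired the heart-failure group can be.
- **Other candidates may help.** Self-reported activity, age, depression and self-efficacy could absorb part of a heart-failure effect if they survive selection. The calculation assumes that they absorb none.
- **The Protocol is silent on stratification.** It does not say that allocation was unstratified, and that should not be inferred.
- **The rationale is not confined to ischaemic disease.** The Background does refer to "preventing secondary cardiac events in patients with ischemic heart disease", but it frames the research gap around people who complete rehabilitation generally. Inclusion 2 fits that, so the mix of diagnoses is not a departure from the rationale.

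What the reply does not answer is that the SAP gives greater precision as its reason for adjusting. It then offers no cardiac or walking-capacity variable, in a design with no baseline step count, although both diagnosis and baseline walk distance should be to hand.

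**Conclusion.** The point holds as a modest matter of precision and of balance in the allocation actually obtained. The stronger reading, that heart-failure imbalance biases the step comparison or inflates its overall type I error, is not supported. Under the assumed values a typical chance imbalance moves the unadjusted difference by about 80 to 360 steps/day, against a standard error of about 775 that already includes this variation. Adjustment lowers that standard error by about 0.5% to 11%, less about 0.9% for the extra term. The benefit is real only if heart-failure patients are reasonably numerous and walk considerably less than the others, and the documents establish neither. The case for acting is that the change is cheap and fits the SAP's own purpose, not that the current analysis is invalid.

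**What to change.** 1. Report qualifying diagnosis by arm in the baseline table.
2. Add a heart-failure indicator (ejection fraction at or below 35%, coded yes/no whatever other qualifying diagnoses are present) as a fixed term in the step-count and six-minute-walk models, outside the stepwise selection and kept whatever its p-value. The coding rule is needed because the criterion's categories can overlap in one person.
3. In the step-count model, baseline six-minute walk is a sound addition or alternative. It measures walking capacity directly and is already collected in both arms.
4. The SAP is in the past tense and comments on results. If outcomes have been seen, label the adjusted models as sensitivity analyses beside the existing ones.

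The cost is one degree of freedom per model for each added term and a sentence or two in the SAP. That the diagnosis is on file is inferred from the need to apply inclusion 2, and should be confirmed. Stratified randomisation appears to come too late. An analysis restricted to participants without heart failure is not recommended: it would still contain valve patients and could drop ischaemic ones. No eligibility, visit or treatment rule changes.

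### The primary outcome, daily steps, appears to be measured by a synced Fitbit in one arm and a pedometer with a handwritten diary in the other, so any counting or recording offset cannot be separated from the package effect.

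*Protocol*

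**What the plan says.** **Outcome.** The SAP (Statistical Analysis) takes daily step count over 60 days as the primary outcome and compares the groups with a linear mixed-effects model. It does not say which device produced the counts. Aim 1 in the protocol's Background says: "The MVN group will have more physical activity (measured by an activity tracker" (the closing bracket follows in the text).

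**Devices.** In the protocol section Both Usual Care and MVN Intervention groups, everyone receives a tracker, but of different kinds:

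- MVN: "Participants randomized to the intervention group will receive a Fitbit and instructions on how to sync their data".
- Control: "Participants randomized to the control group will receive a basic pedometer with a paper diary to record their step counts each day".

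The Study Activities table marks "Activity tracker" for both arms and "Step count diary" for Usual Care only. Both are scheduled for the intervention period, with no baseline entry. The aims describe the trial as "comparing the intervention group (MVN app and Fitbit) to the control group (pedometer only".

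**Timing.** Under MVN Group Only: "During the final week of outpatient cardiac rehabilitation, the MVN application will be downloaded".

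**Adjustment and missing data.** The SAP's candidate covariates are demographic, psychosocial and self-reported activity variables. None concerns device, wear time or pre-randomisation steps. Its missing-data paragraph covers covariates only.

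**The concern.** Randomisation balances the people in the two arms. It does not balance instruments that are handed out by arm. If the Fitbit and the pedometer register different counts for the same walking, or if synced and handwritten records differ, that difference enters the primary estimate as if it were activity.

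Extra walking prompted by wearing a Fitbit is a different matter. The aims make the Fitbit part of the intervention, so that walking is treatment effect. The concern is only with a different count for the same walking.

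Such an offset could create, inflate or hide a step difference. Averaging over 60 days or enrolling more participants narrows the standard error and leaves the offset in place. Early tracker days cannot serve as an untreated baseline, because the app is installed before rehabilitation ends.

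A secondary worry is that a blank diary day and an unsynced day arise in different ways, so the set of recorded days may differ by arm.

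**Working it through.** The documents give no step mean, SD, target difference or sample-size derivation, so there is no stated figure to reproduce.

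**1. Can the model separate device from arm?** Write the expected difference in recorded steps as

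recorded difference = package effect + device and recording offset.

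Device equals arm for every participant. A design matrix with intercept, arm and device has rank 2 with 3 columns. Expanded to 60 daily records with a day term, it has rank 3 with 4 columns. The two terms cannot be estimated separately, and none of the listed covariates changes that. Self-reported activity is a covariate, not a calibration of either device.

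**2. False positives, scale-free.** Inputs: up to 60 participants (protocol, Selection of Subjects / Setting), taken as 30 per arm (assumed, since the ratio is not stated); two-sided alpha 0.05 (SAP); an offset that shifts the difference without changing its standard error (assumed). A two-sample t-test on person means has 58 df and critical t = 2.0017. With no true effect, the rejection rate is the two-tailed noncentral t probability with noncentrality = offset / SE:

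| Offset / SE | Rejection rate |
|---|---|
| 0 | 5.0% |
| 0.25 | 5.7% |
| 0.5 | 7.8% |
| 1 | 16.6% |
| 1.5 | 31.4% |
| 2 | 50.3% |

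**3. How much of an observed difference must be offset to lose significance?** Removing a share f leaves t = (1 − f) × t_obs, so the tipping share is f = (t_obs − 2.0017) / t_obs.

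| Observed p | t_obs | Tipping share |
|---|---|---|
| 0.04 | 2.101 | 4.7% |
| 0.02 | 2.392 | 16.3% |
| 0.01 | 2.663 | 24.8% |
| 0.001 | 3.466 | 42.3% |

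With 48 df instead of 58, the shares at p = 0.04, 0.02, 0.01 and 0.001 are 4.8%, 16.5%, 25.0% and 42.6%.

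**4. Illustration in steps (assumed values, not trial evidence).** Take a mean of 7,000 steps/day and a between-person SD of 3,000.

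- SE = 3,000 × √(2/30) = 774.6.
- An offset of 5% is 350 steps: 350 / 774.6 = 0.452, rejection rate 7.3%.
- An offset of 10% is 700 steps: 700 / 774.6 = 0.904, rejection rate 14.4%.
- Over means of 6,000 to 8,000 and SDs of 2,500 to 3,500, the ranges are 6.2–9.4% and 10.0–23.0%.
- If covariates explain 10%, 20% or 30% of between-person variance, the 700-step offset gives 15.5%, 16.9% or 18.6%. Adjustment makes a fixed offset more visible to the test.
- On this scale 1 SE is 11% of the mean (775 / 7,000) and 2 SE is 22% (1,549 / 7,000). The 50.3% in step 2 therefore needs an offset of more than twice the 10% case.

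A simulated daily random-intercept model (1,000 trials per setting, 60 days, assumed within-person daily SD 2,500) rejected in 4.4%, 7.0% and 15.7% of trials at offsets of 0, 350 and 700 steps. That agrees with the t-test figures within simulation error.

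**5. The opposite direction.** The difference detectable with 80% power is 2,207 steps. If the MVN count is low by a fixed 350 or 700 steps, power falls to 65% or 48%. If under-counting is instead proportional and 7,000 is the control mean, the MVN mean is 7,000 + 2,207 = 9,207. Losses of 5% or 10% are then 460 or 921 steps, and power is about 60% or 37%.

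**6. Missing days (secondary).** Overstatement of an arm's mean = blank fraction × step deficit on blank days. With 20% of days blank in one arm only and a deficit of 1,000 to 3,000 steps, this is 200 to 600 steps/day, or 2.9% to 8.6% of 7,000. It favours whichever arm has the blanks, so it can add to a device offset or cancel it.

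**The case against.** The strongest reply is that the trial compares two openly described packages and the device belongs to them. That stands for behaviour prompted by the Fitbit. It does not stand for counting error, which is not an effect on the participant.

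Second, nothing in the documents shows that an offset exists, how large it is or which way it runs, and the step source is itself inferred because the SAP names no device. Both statements are true. One part of the SAP was not in the text reviewed, so a device statement or valid-day rule there cannot be excluded. The point survives because it concerns what the plan can identify: nothing in the text available would detect an offset or rule one out.

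Third, the scale-free figures hold for any two-arm t-test with 58 df and say nothing particular to this trial. That is fair. They show sensitivity and are not evidence of bias.

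Fourth, a mixed model on daily counts is valid for days missing at random if correctly specified. This stands, and the 200 to 600 step shift applies only if blank days are lower in steps for reasons the model does not capture.

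Finally, the 6-minute walk test (6MWT) is scheduled identically in both arms. It is useful support, but it measures exercise capacity and cannot calibrate daily steps.

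**Conclusion.** The concern holds and must be addressed, because it affects attribution of the primary outcome. On the devices the protocol describes, the step contrast cannot be assigned to the package alone. This conclusion rests on the exact coincidence of device and arm, and on the inference that these devices supplied the analysed steps. It does not rest on the assumed means and SDs.

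The size of any offset is unknown. With 30 per arm, a modest one would matter for a borderline result: at p = 0.04 less than 5% of the observed difference need be offset for significance to be lost. A strong result is sturdier: at p = 0.001 the share is 42%. In the step illustration, a 10% offset gives 10–23% false positives over the assumed range. The missing-day question is secondary and conditional.

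**What to change.** **Before enrolment, or in a future trial.** Measure the primary outcome in both arms with the same instrument and recording method. For example, give everyone the same basic pedometer and diary and keep the Fitbit as an intervention component. Instruct MVN participants to write down the pedometer reading and not the Fitbit count, and report recorded pedometer days by arm. The cost is about 30 more pedometers and diaries. MVN participants would carry a second device and keep a diary, which adds burden and may itself change activity. They may also wear the pedometer less or copy Fitbit counts, so the offset is reduced but not guaranteed to be zero.

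**With data already collected**, as the SAP's past tense indicates, the design cannot be repaired. Keep daily steps as the primary outcome and:

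1. State the device behind the counts, apply one valid-day rule to both arms, and report recorded days by arm.
2. Report a tipping-point analysis: the offset, in steps/day and as a share of the observed difference, at which the conclusion changes. Secondarily, give the arm-specific missing-day shift that would do the same.
3. Limit the conclusion along these lines: *Steps were measured with different devices in the two arms; the difference reflects the package effect plus any device or recording offset, and loses significance if X% of it is offset.*
4. Present the 6MWT, already the secondary outcome, as tracker-independent support and not as a replacement primary outcome. Change in questionnaire physical activity ("Questionnaires will ask about health care utilization, physical activity, quality of life, and self-efficacy") can be added as weaker support, since it is self-reported by participants who know their arm.

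This costs some analyst time and a more cautious step-count conclusion. It exposes a possible offset but does not remove it.

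### Daily steps have no pre-randomisation value, and the step model leaves out the baseline 6-minute walk and may drop self-reported activity, so the comparison is avoidably imprecise

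*Protocol*

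**What the plan says.** The SAP (Statistical Analysis) defines the primary comparison: "We analyzed the primary outcome of step count difference between the two groups over 60 days fitting linear mixed-effects models", with one step count per day as the response.

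The Protocol (Both Usual Care and MVN Intervention groups) hands out the step-counting devices according to allocated arm: "Participants randomized to the intervention group will receive a Fitbit and instructions on how to sync their data", and "Participants randomized to the control group will receive a basic pedometer with a paper diary to record their step counts each day". The Study Activities table agrees: "Activity tracker X X Intervention period". The step diary row carries the same interval. Questionnaires, blood pressure and heart rate, weight and the 6-minute walk are all scheduled at baseline and month 2.

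The 6-minute walk is therefore available at baseline in both arms; the Protocol's list for both groups includes "Baseline clinical measurements, including a 6 minute walk".

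The SAP's candidate covariates for the step model are "age, gender, working status, college or higher education, relationship status, depression, self-efficacy, and self-reported PA". A step-wise procedure selects among them and keeps only significant terms; its stated purpose is to sharpen the estimate of the treatment effect. The 6-minute walk appears in the SAP only as a secondary outcome, analysed as a standardised change from baseline.

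**The concern.** People differ in how much they habitually walk, and that difference persists through the follow-up period. Sixty readings per person average out day-to-day noise but do not reduce the variance between people, and with at most 60 participants that variance limits the precision of the comparison. A covariate that predicts a person's step level removes part of it.

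A baseline step count would be the natural covariate, and none exists. The first tracker days cannot stand in for it, because they follow randomisation and, in the MVN arm, coincide with prompts and feedback. That makes the other baseline activity-related measures more important. The plan leaves one of them out (the 6-minute walk) and makes the other (self-reported activity) depend on a significance test. At stake is precision that could be had from data already collected, and assurance that a chance difference in activity between the arms is at least partly adjusted for.

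**Working it through.** The documents give no power calculation, standard deviation, correlation or allocation ratio, so there is no stated figure to reproduce.

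**Inputs from the documents.** Up to 60 participants (Protocol, Selection of Subjects / Setting); two-sided alpha 0.05 (SAP); eight candidate covariates, kept only if significant (SAP).

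**Assumptions.** 30 per arm; the between-person standard deviation (SD) of mean daily steps is set to 1; the correlations are the ranges shown; the illustrative effect is 0.5 SD.

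**1. Unadjusted standard error (SE).** √(2/30) = 0.258 SD.

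**2. Effect of one fixed covariate, against a model with no covariates.** A covariate with correlation r to the outcome multiplies the SE by √(1 − r²). The equivalent sample size is 60/(1 − r²). Power is Φ(0.5/SE − 1.96).

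| r | SE multiplier | SE reduction | Equivalent N | Power at 0.5 SD |
|---|---|---|---|---|
| 0 | 1.000 | – | 60 | 49% |
| 0.3 | 0.954 | 5% | 60/0.91 ≈ 66 | 53% |
| 0.4 | 0.917 | 8% | 60/0.84 ≈ 71 | 56% |
| 0.5 | 0.866 | 13% | 60/0.75 = 80 | 61% |

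The percentage reductions do not depend on the SD in steps per day.

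**3. Gain from the 6-minute walk when self-reported activity is already in the model.** Let s be the correlation of self-report with steps, w that of the 6-minute walk with steps, and c the correlation between the two. Then R² = (s² + w² − 2swc)/(1 − c²), and the SE ratio is √[(1 − R²)/(1 − s²)]. The grid is s = 0.2 to 0.4, w = 0.3 to 0.6, c = 0.2 to 0.4.

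- Smallest gain (s = 0.4, w = 0.3, c = 0.4): R² = (0.16 + 0.09 − 0.096)/0.84 = 0.183; ratio √(0.817/0.84) = 0.986, about 1%.
- Largest gain (s = 0.2, w = 0.6, c = 0.2): R² = (0.04 + 0.36 − 0.048)/0.96 = 0.367; ratio √(0.633/0.96) = 0.812, about 19%.

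These ratios ignore the cost of estimating one more coefficient. With 60 participants the residual degrees of freedom fall from 57 to 56, so that cost is about √(57/56) = 1.009, or 1% of the SE. At the bottom of the range the addition roughly breaks even.

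**4. Chance that self-reported activity is kept.** By Fisher's z with n = 60, the probability of p < 0.05 is approximately Φ(atanh(r)·√57 − 1.96):

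- r = 0.2: 33%
- r = 0.3: 65%
- r = 0.4: 89%

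This treats the term on its own; the full step-wise procedure may behave differently.

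**5. Size of chance imbalance.** The arm difference in any baseline trait has SE 0.258 SD, so its 95% range is ±0.51 SD, and it exceeds 0.25 SD in about 33% of randomisations. Only r times the imbalance carries into the step comparison: at r = 0.5, 0.5 × 0.51 ≈ ±0.25 SD.

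**The case against.** The strongest reply is that a randomised comparison without a baseline value of the outcome is valid. That stands. Chance imbalance in activity is already reflected in the SE, the confidence interval and the 5% test. It is not a bias, and the shift in step 5 of the working is the same lost precision seen from another side.

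A reader might infer that imbalance in activity cannot be corrected at all. The SAP does not support this: self-reported activity is a candidate and, if retained, corrects part of it. What is missing is correction on the outcome's own scale or by an objective measure, and any guarantee that the self-report term stays.

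The table also compares with a model that has no covariates, whereas the SAP's model may already hold several. For the 6-minute walk the fairer figure is the increment in step 3, which may be small. The walk measures functional capacity rather than habitual activity, so a high correlation with daily steps should not be presumed.

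A reader might also conclude that the plan should have required a step-count run-in. That is a design trade-off, not an error. A pedometer baseline in everyone would be followed by a Fitbit outcome in one arm, so the outcome's own scale would not be assured there, and any offset between devices would remain confounded with arm. The Protocol also sets up the app in the final week of rehabilitation, so an earlier baseline week would fall during the supervised programme and might predict later walking poorly.

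Finally, the SAP is written in the past tense, which suggests that the analysis was complete. If so, pre-specification is no longer possible.

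**Conclusion.** The point holds as a matter of efficiency, not validity. Three facts are clear from the documents: no pre-randomisation steps exist in either arm, the baseline 6-minute walk is not a candidate in the step model, and the only activity covariate is self-reported and conditional on significance. The treatment comparison is unbiased by chance imbalance but less precise than the collected data may allow.

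The size is uncertain. It runs from 5% to 13% of the SE for one fixed covariate against no covariates, and from about 1% to 19% for the 6-minute walk added to retained self-reported activity. All of these rest on assumed correlations and equal arms; the omission itself does not. Larger gains would need a baseline step count, which this trial does not have.

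One ambiguity remains: the SAP does not say that self-reported activity is the baseline value. The visit schedule makes that likely. A month-2 value would come after randomisation, and adjusting for it could remove part of the treatment effect.

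**What to change.** In the SAP's daily-step mixed model, include baseline 6-minute walk distance and baseline self-reported physical activity as fixed covariates regardless of significance, and state that both are baseline values. If the primary analysis is already done, report this model as a labelled sensitivity analysis beside the existing result. In either case, report the absence of baseline steps as a limitation.

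The cost is one or two sentences in the SAP, one rerun of the model, and two model coefficients. No new data are needed. The baseline walk should join the existing multiple imputation in case some values are missing; the SAP's missingness figures cover its listed covariates, which do not include the walk.

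A run-in with a common device before randomisation is something to weigh for a future trial and is not part of this change.
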